Title: Evaluation of the Necessity of Operative Irrigation and Debridement: Pediatric Randomized trial of type One Open Fractures (PROOF)

Author: [name]

Version Date: 06/01/2015

A. Scientific Aims:

Clinical Trial Portion:

1. Do patients with type one open fractures treated in the emergency department with irrigation have a non-inferior rate of infections compared to those treated in the operating room with formal irrigation and debridement? The response variable will be the presence of an infection in children with open fractures.
2. Do patients with type I open fractures who are treated nonoperatively have a non-inferior time to bone healing when compared to those treated operatively? The response variable will be time to clinical and radiographic fracture healing.

Hypothesis: Minor open fractures in children can be safely treated in the emergency room with irrigation, closed reduction and home antibiotics without an increased risk of infection or a longer time to healing.

- a. Null Hypothesis: Open fractures treated in the emergency room will have a higher rate of infection, and a longer time to complete healing.

Survey Portion:

3. What are the current attitudes among members of the Pediatric Orthopaedic Society of North America (POSNA) toward the treatment of type one open fractures in the pediatric population?

Hypothesis: There will be no consensus in the treatment of type 1 open fractures in the pediatric population in regards to whether or not formal irrigation and debridement is necessary, antibiotic use, and timing for fractures.

A. Significance:

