The family will be instructed to look for signs of infection including increased pain, fevers, or odor coming from the cast. All patients will follow up 5-7 days after the injury where the cast will be windowed and the wound examined. This follow-up appointment is standard of care for all Type I open fractures. Infection will be defined as the Surgical Site Infection by the CDC (see Supplementary information section) guidelines. Signs of infection such as erythema and wound drainage will be treated at the discretion of the attending orthopaedic surgeon with additional antibiotics, local wound care, or formal operative debridement. If no signs of infection are noted then the cast will be repaired. Radiographs will be obtained, as is the standard of care, at all follow up visits. Future follow up visits will not include a routine wound examination unless clinically indicated – fevers, increasing pain, foul odor from cast, etc.

Follow up appointments will be standard of care (non-research related) and will be at approximately 1, 2, 4, 6, 12 and 24 weeks post op.

Informed Consent Process:

If the patient agrees to participate he/she will be formally consented and randomized by calling the study coordinator. The study coordinator, or a representative, will be available 24 hours/day to provide the Parent Permission (consent) form, Adolescent Assent form, and HIPAA Authorization form (if separate from the consent form). At each institution, each participant will be consented using the IRB approved consent and assent forms and HIPAA Authorizations of their institution. The study coordinator, or representative, will have digital copies of each participating institutions' consent forms, assent forms, and HIPAA Authorizations in order to obtain consent remotely at that institution. The study coordinator, or representative, obtaining consent will be listed on the authorized personnel list of the institution that joins the study and has IRB approval to obtain consent with this electronic, remote procedure.

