(Specific Aim 2) Union of the fracture will be determined by radiographic parameters of callous being on three of four sides of bone without tenderness to palpation. The radiographs will be read by the attending orthopaedic surgeon at each clinic visit to determine treatment. Loss of reduction will be noted but will not be considered a complication since it can occur whether or not operative debridement was performed. A revision reduction can be performed at the attending orthopaedic surgeon's discretion. In the final analysis phase, an orthopaedic surgeon, blinded to the treatment, at Lurie Children's will be utilized to review all of the patient's radiographs to determine bridging callous on three sides of the bone. This reviewer will be blinded to the patient's name, treatment group but will have access to the length of time since the fracture occurred. Additional procedures or deviations from the protocol will be noted. We will

also carefully examine the rates of anesthesia and sedation related complications including nausea and vomiting, respiratory depression, aspiration, hoarseness, and emergence agitation.

Sample size assumptions and estimates:

This will be a non-inferiority trial as we attempt to demonstrate that ED management is not inferior to OR management.

For the binary outcome of infection (**Specific Aim 1**), we estimate an infection rate of 1% in the reference (OR) group since the literature notes an infection rate between 0% and 5%. Based on a survey of pediatric orthopedic surgeons, an acceptable margin of non-inferiority can be estimated at approximately 4% (i.e., accept a 5% infection rate in the ED group), as the survey suggests surgeons will accept a 5% infection rate in order to avoid formal operative treatment of children with open fractures. We will test the following hypotheses: $H_0: P_T - P_C \geq \Delta$ vs. $H_1: P_T - P_C < \Delta$. In order to test these hypotheses in a non-inferiority design at the one-sided 2.5% level of significance, we will construct a two-sided 95% confidence interval for the difference in proportion of infections ($P_T - P_C$) across the two groups. If the upper confidence limit is less than our acceptable margin of non-inferiority ($\Delta=4\%$), then we would conclude ED management is not inferior to OR management with respect to infection rates.

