The following are power estimates based on 10000 simulations under the above conditions for various feasible sample sizes. We also obtained power estimates for the scenario involving a 2% infection rate in the control group (OD).

Sample size/arm	Reference Proportion	Power ($\Delta=0.03$)	Power ($\Delta=0.04$)	Power ($\Delta=0.05$)	Power ($\Delta=0.06$)
70	0.01	0.5091	0.6766	0.8536	0.866
80	0.01	0.5164	0.8107	0.8382	0.9434
90	0.01	0.4865	0.786	0.8734	0.9489
100	0.01	0.7416	0.7878	0.9254	0.9616
110	0.01	0.6994	0.8383	0.9245	0.976
120	0.01	0.6926	0.894	0.9437	0.9763
130	0.01	0.714	0.8738	0.9621	0.981
140	0.01	0.6907	0.8783	0.9624	0.99
150	0.01	0.7606	0.9111	0.9748	0.9928
160	0.01	0.8221	0.9394	0.9816	0.997
170	0.01	0.795	0.9427	0.9842	0.998
180	0.01	0.821	0.9339	0.9876	0.9984
190	0.01	0.8147	0.9573	0.9936	0.9987
200	0.01	0.848	0.9629	0.9928	0.9987
210	0.01	0.8503	0.9669	0.9941	0.9995
220	0.01	0.8675	0.9743	0.9961	0.9992
130	0.02	0.4748	0.6378	0.8123	0.9066
140	0.02	0.4906	0.6922	0.8385	0.9288
150	0.02	0.5051	0.7048	0.8785	0.9466
160	0.02	0.5642	0.7452	0.8678	0.9593

170	0.02	0.5458	0.7621	0.8958	0.9679
180	0.02	0.5651	0.7737	0.9165	0.9682
190	0.02	0.5864	0.8088	0.9317	0.9733
200	0.02	0.5865	0.8005	0.9275	0.9807
210	0.02	0.6349	0.8346	0.943	0.9833
220	0.02	0.61	0.842	0.9504	0.9868

For outcome of healing time (**Specific Aim 2**), most fractures have a healing time of 6 weeks with an estimated standard deviation of 1 week. We will again try to show ED management is not inferior with respect to healing time when compared to OR management, assuming a margin of non-inferiority of one week ($\Delta=1$). Assuming a one-sided 0.025 level of significance and power ($1-\beta$) equal to 0.90, the number of subjects required per treatment group can be calculated as follows:

$$H_0: \mu_C - \mu_T \geq \Delta \quad \text{vs.} \quad H_1: \mu_C - \mu_T < \Delta$$

$$N = \frac{2(Z_{\alpha} + Z_{1-\beta})^2 \sigma^2}{\Delta^2}$$

$$N = \frac{2(1.96 + 1.282)^2 1^2}{1^2} \qquad N = 21$$

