We will use an independent two-sample confidence interval for binomial proportions comparing infection rates between the two treatment arms. If the upper limit of a two-sided, 95% confidence interval is less than the margin of non-inferiority, we will have evidence that ED management is not inferior to OR management. Similarly, an independent two-sample confidence for difference in mean healing time will be constructed and used in the same manner to determine evidence of non-inferiority. Both large sample, normal approximation methods and exact methods will be explored. Descriptive data will be used to relay anesthesia complications, additional procedures and significant infections. Primary analysis will be based on the "as treated" principle, and an intent-to-treat analysis will also be conducted. We expect almost no cross-over in the initial 24 hours after injury. We will also use Kaplan-Meier estimation to create curves comparing cumulative incidence of infection as well as time to healing for the duration of study follow-up.

Data Security:

Research Electronic Data Capture (REDCap)

REDCap is a secure application used for managing online databases for collecting research data. The software allows data to be stored over a secure web connection with authentication and data logging features. The database creates a log of all activity including information such as the date, time and user who performed the action. The database is password protected and only approved users are able to access projects through REDCap. Data for all sites involved in this multi-center project will be stored in this electronic database. PIs and research coordinators from each site

will be assigned Northwestern University Affiliate NetIDs which will give them access to REDCap through Northwestern University Clinical and Translational Sciences Institute (NUCATS). Once these NetIDs are granted, the research coordinator at Lurie Children's will then add these individuals to the REDCap project.

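### The formal Aim 2 (healing time) hypotheses have the difference the wrong way round: read literally, a slower emergency-department arm is declared non-inferior

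*Combined protocol and SAP*

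**What the plan says.** All references are to the combined protocol and SAP.

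- **Section A, Scientific Aims.** The stated null is "Open fractures treated in the emergency room will have a higher rate of infection, and a longer time to complete healing". The result to be ruled out is therefore slower healing in the ED arm.
- **Section E, Sample size assumptions and estimates, Aim 1.** The OR group is the reference, so C is OR and T is ED. The infection alternative is "H_1: P_T - P_C < \Delta", which is ED minus OR. A higher value is worse.
- **Same subsection, Aim 2.** The prose reads "We will again try to show ED management is not inferior with respect to healing time when compared to OR management", with a margin of one week. The displayed alternative is "H_1: \mu_C - \mu_T < \Delta", and the paired null is that μ_C − μ_T is at least Δ. The subtraction is now OR minus ED. The assumption is that "most fractures have a healing time of 6 weeks with an estimated standard deviation of 1 week", and the result is 21 per group.
- **Section E, Data Analysis (after Data management).** For infection, ED is non-inferior if the upper limit of the two-sided 95% interval lies below the margin. For healing, an interval for the "difference in mean healing time will be constructed and used in the same manner to determine evidence of non-inferiority". The direction of subtraction is not named.

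**The concern.** A non-inferiority test on an outcome where larger is worse has to rule out an excess in the new treatment. The displayed Aim 2 null instead says that OR takes at least a week longer than ED, that is, that ED is better by the full margin. Rejecting it shows only that ED is not a week or more faster. It says nothing about ED being slower.

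Healing time is one of the trial's two clinical aims, and the displayed line is the only formal version of its test. An analyst who programs from that line, and who finds no direction in the Data Analysis section to override it, would apply a pass/fail rule that accepts any delay in the ED arm and penalises a benefit.

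**Working it through.** **Inputs.** From the Aim 2 sample-size text: margin Δ = 1 week, σ = 1 week, one-sided level 0.025, power 0.90. From the overall sample-size conclusion: 150 per arm. From the Aim 1 text: C = OR, T = ED.

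**Step 1: reproduce the plan's figure.** N = 2(1.96 + 1.282)² × 1² / 1² = 21.02, which the plan gives as 21. Strict rounding up gives 22, a difference of no consequence with 150 per arm planned. The formula assumes a true difference of zero and uses Δ squared, so the direction of subtraction does not enter. That is why the sample-size check could not have exposed the reversal.

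**Step 2: the two rules.** Let d = μ_T − μ_C (positive means ED is slower) and SE = σ√(2/n).

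- Literal rule: declare non-inferiority if the upper 95% limit for OR minus ED is below 1. Probability = Φ((1 + d)/SE − 1.96).
- Corrected rule: declare non-inferiority if the upper 95% limit for ED minus OR is below 1. Probability = Φ((1 − d)/SE − 1.96).

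**Step 3: put the numbers in.** At n = 150, SE = √(2/150) = 0.1155 and 1/SE = 8.66.

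| True difference, ED minus OR | Literal rule | Corrected rule |
|---|---|---|
| 1.25 weeks faster | Φ(−2.17 − 1.96) = 0.002% | about 100% |
| 1 week faster | Φ(0 − 1.96) = 2.5% | Φ(17.32 − 1.96), about 100% |
| equal | Φ(8.66 − 1.96), about 100% | the same |
| 0.5 week slower | about 100% | Φ(4.33 − 1.96) = 99.1% |
| 1 week slower | Φ(17.32 − 1.96), about 100% | Φ(0 − 1.96) = 2.5% |
| 2 weeks slower | about 100% | Φ(−8.66 − 1.96), about 0% |

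At n = 21, SE = √(2/21) = 0.3086. With equal arms both rules pass Φ(3.24 − 1.96) = 90.0% of the time, the plan's stated power. With ED one week slower, the literal rule passes Φ(6.48 − 1.96), about 100%, and the corrected rule 2.5%.

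**Step 4: one data set under both rules.** Suppose ED heals two weeks slower on average at 150 per arm. The half-width is 1.96 × 0.1155 = 0.23 week. The interval for ED minus OR is 1.77 to 2.23, which is above the margin, so ED fails. The same interval written as OR minus ED is −2.23 to −1.77. Its upper limit is below 1, so the literal rule declares ED non-inferior.

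**Step 5: could the labels rescue the line?** T and C are not redefined for Aim 2. If T were OR and C were ED, the Aim 2 line would be right, but the same labels would reverse Aim 1, where OR is named as the reference. The reversal appears in both the null and the alternative, so a fault in reading the PDF is not a plausible explanation.

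**The case against.** The strongest reply is that this is a slip in a sample-size derivation that changes nothing computed there. The Scientific Aims and the introductory sentence make the intended direction plain, and the Data Analysis section does not repeat the reversed line. Most of this stands. The intended direction is clear, N is unaffected, and nothing shows that the investigators mean to run the reversed test. What does not follow is that the line can be left. It is the only formal statement of the Aim 2 test, and the Data Analysis section names no direction that would overrule it.

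Three stronger readings are tempting, and the documents do not support them.

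- **That the trial could not detect slower healing.** The Data Analysis section plans a confidence interval for the difference in means and Kaplan-Meier curves for time to healing, and the Final analysis section repeats both. A slower ED arm would be visible in these whichever way the difference is signed.
- **That the line is contradicted throughout the plan.** The direct conflicts are with the Scientific Aims null and with the Aim 2 prose. The Aim 1 hypotheses concern infection, and the Data Analysis wording carries the infection rule over without naming a direction. Both support the correction by parallel only.
- **That the visit schedule makes the healing comparison invalid.** Follow-up visits "will be at approximately 1, 2, 4, 6, 12 and 24 weeks post op", and the documents supplied do not state how union is dated when it falls between two visits. This is a missing detail, not part of the error. First recording at the visit where union is seen is a natural reading, although it is not written as a rule.

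**Conclusion.** The Aim 2 hypotheses are wrong as written and should be corrected before anyone programs the analysis. With SD 1 week, 150 per arm and the normal approximation, the probability of declaring non-inferiority at a true one-week ED delay is about 100% under the literal line and 2.5% under the corrected one; at a true one-week ED advantage the two figures change places. These figures rest on the plan's own inputs and assume that an analyst follows the displayed line literally. The error is confined to the formal pass/fail declaration: the sample size, the planned estimate with its interval, and the curves are unaffected. Because the intended direction is clear elsewhere, this is a one-line correction of a decision rule, not a fault in the trial's design.

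**What to change.** 1. In Sample size assumptions and estimates, Aim 2, write H0: μ_T − μ_C ≥ 1 week against H1: μ_T − μ_C < 1 week, and state that T is ED and C is OR. Keeping OR minus ED with a bound of −1 week (H1: μ_C − μ_T > −1 week) is algebraically the same, but ED minus OR matches Aim 1.
2. In Data Analysis, state that non-inferiority on healing time is concluded only if the upper limit of the two-sided 95% confidence interval for ED minus OR mean healing time is below 1 week.

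The cost is one corrected line and one added sentence. N = 21, the 150 per arm, the visits and the data collected all stay as they are.

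Optional, and separate from the error: add one sentence saying what healing date is assigned when union is first seen at a visit. The union definition ("Union of the fracture will be determined by radiographic parameters of callous being on three of four sides of bone without tenderness to palpation") gives no dating rule, and the assumed mean of 6 weeks falls at the start of the gap between the visits at about weeks 6 and 12.

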Our results suggest that a **sample size of 150 per group (300 total)** would provide 91% power to detect non-inferiority of emergency room management when compared to operating room treatment in the type one open fractures under the assumptions outlined above. We have accepted a 5% infection rate (4% shift from the hypothesized reference rate). If the baseline infection rate is 2%, this study would be adequately powered (87%) to show non-inferiority for a margin of 5% (7% infection rate in the ED arm). As the calculation above illustrates, the study is also well powered to demonstrate non-inferiority with respect to healing time.

Site estimates:

The following sites have provided the initial estimates as to how many patients they feel could be enrolled in a given year: Lurie Children’s = 2/year, Vancouver Children’s Hospital 5/y, Riley Children’s= 2/y, University of Mississippi Medical Center = 9/y, Mary Bridge Children’s Hospital= 12/y, Yale-New Haven Children’s Hospital= 4/y, Carrie Tingley Children’s Hospital= 20/y, Phoenix Children’s Hospital= 20/y, Nationwide Children’s Hospital= 20y, IWK Health Centre, Halifax=4/y, Denver Children’s Hospital=12/y. Texas Children’s Hospital= 12/y, Morristown Medical Center = 2/y, New York University Medical Center = 4/y. Approximate Total= 128/y.

Subject Recruitment:

The number of subjects needed for this trial is large. To date, the pilot study has had an excellent recruitment (80% see below) rate, so we expect similar rates at participating centers.

Currently, with the 14 sites who have agreed to participate thus far, the expected recruitment is 128 patients per year. We plan to add 4-6 more sites during the Planning Grant Period which would expand the projected total recruitment to 160 patients per year. Therefore, when the study is at full capacity, we conservatively anticipate recruiting 120 patients per year (assuming 75% recruitment rate) over the 3 year grant period, for a total of 360 patients, which surpasses the calculated 300 patients needed for adequate statistical power. We are accepting and powering for a 5% infection rate in the ED arm. If we were to accept a 6% infection rate (i.e., a 5% margin of non-inferiority) then we would require only 190 patients. For a 7% infection rate ($\Delta=0.06$), we will need 150 patients. If recruitment is lower than expected, we could accept a larger

margin of non-inferiority given the large range of type I open fracture rate (0-10%) in the literature.

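### At 150 per arm, 91% power and a one-sided 2.5% error level cannot both hold for the infection endpoint, and the plan does not say which confidence interval decides

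*Combined protocol and SAP*

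**What the plan says.** All references are to section E (Methods) of the combined protocol and SAP.

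- **Sample size assumptions and estimates** sets the infection rate in the operating-room (OR) arm at 1% and the margin at 4 percentage points, so that a 5% rate in the emergency-department (ED) arm is the limit. The test is run "at the one-sided 2.5% level of significance, we will construct a two-sided 95% confidence interval", and non-inferiority follows if the upper limit is below the margin.
- The power table is introduced with: "The following are power estimates based on 10000 simulations under the above conditions for various feasible sample sizes". It does not say which interval was simulated. At 150 per arm, 1% rate, margin 4%, the entry is 0.9111.
- The text concludes that 150 per group "would provide 91% power to detect non-inferiority of emergency room management when compared to operating room treatment". For a 2% baseline it adds that "this study would be adequately powered (87%) to show non-inferiority for a margin of 5" percentage points.
- **Subject Recruitment** gives fallbacks. With a 5% margin, "then we would require only 190 patients"; with a 6% margin, 150. It projects recruitment "for a total of 360 patients, which surpasses the calculated 300 patients needed for adequate statistical power".
- **Data Analysis** (after Data management) says of the interval only this: "Both large sample, normal approximation methods and exact methods will be explored". It names no exact method and makes none decisive.

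**The concern.** At 150 per arm and a 1% rate, about 1.5 infections are expected in each arm. With counts this small, the Wald interval is too narrow when it matters. A chance low count in the ED arm lowers both the estimated difference and its estimated standard error, so the upper limit falls below 4% too easily. If the 91% comes from such an interval, the power is partly bought with excess false-positive error.

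Two things are at stake. If Wald decides, the chance of declaring a truly inferior treatment non-inferior is well above the level the protocol promises. If a method that keeps the level decides, the trial has much less power than stated. Because the choice is left open, it could be made after the counts are known, and at these counts the choice often determines the conclusion.

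**Working it through.** **Inputs.** From Sample size assumptions and estimates: one-sided level 2.5%, margin Δ = 0.04, OR rate 1%, n = 150 per arm. The true ED rate used for power is not stated; I take it as equal to the OR rate, and the match in step 1 supports this. All results are full enumerations of two independent binomials, with no dropout.

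**1. Reproduce the plan's figure.** The Wald rule declares non-inferiority if

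p_ED − p_OR + 1.96·√[p_ED(1−p_ED)/n + p_OR(1−p_OR)/n] < 0.04.

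For example, 3 ED and 1 OR infections give 0.0133 + 0.0259 = 0.0392, which passes. The largest ED count that passes, by OR count:

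| OR infections | 0 | 1 | 2 | 3 | 4 | 5 |
|---|---|---|---|---|---|---|
| Wald | 2 | 3 | 3 | 3 | 4 | 4 |
| Farrington-Manning score | 1 | 1 | 2 | 3 | 3 | 4 |

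At a 1% rate the OR count is 0, 1, 2, 3, 4 with probability 0.2215, 0.3355, 0.2525, 0.1258, 0.0467 (5 or more: 0.0180). The ED count satisfies:

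| ED count | ≤1 | ≤2 | ≤3 | ≤4 |
|---|---|---|---|---|
| ED rate 1% | 0.5570 | 0.8095 | 0.9353 | 0.9820 |
| ED rate 5% | 0.0041 | 0.0182 | 0.0548 | 0.1256 |

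Wald power = 0.2215×0.8095 + (0.3355+0.2525+0.1258)×0.9353 + 0.0467×0.9820 + about 0.018 (OR count 5 or more) = **0.9105**, against 0.9111 in the table. Over the table's 104 cells (26 rows × 4 margins), Wald matches all within 0.012 and 97 within 0.005. Score and Newcombe intervals match 5 each within 0.012, and Agresti-Caffo 20. The use of Wald is inferred from this match.

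**2. Wald error at the plan's boundary (OR 1%, ED 5%).** The same sum with the 5% row: 0.2215×0.0182 + 0.7138×0.0548 + 0.0467×0.1256 + about 0.003 = **5.2%**, against 2.5% stated. At other OR rates with the 4% margin it is 6.4% (OR 0.5%), 3.7% (2%), 3.4% (3%) and 2.9% (5%).

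**3. Ceiling for any method.** The OR rate is 1% under both hypotheses, so by the Neyman-Pearson lemma the most powerful test uses the ED count alone. Accepting ≤2 uses 1.82% error and ≤3 uses 5.48%. Randomising to exactly 2.5%:

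0.8095 + [(0.025 − 0.0182)/0.0366] × 0.1258 = **0.833**.

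This controls error at one point only. A linear programme over all decision rules, with error at most 2.5% for every OR rate on a grid from 0 to 10%, gives **0.785**; restricting the range to 0–5% gives the same value.

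**4. Specific intervals, 150 per arm, margin 4%.**

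| Interval | Power at 1%/1% | Error at OR 1%/ED 5% |
|---|---|---|
| Wald | 91.1% | 5.2% |
| Hauck-Anderson | 86.8% | 3.9% |
| Agresti-Caffo | 83.4% | 2.7% |
| Profile likelihood | 78.1% | 2.7% |
| Farrington-Manning, Miettinen-Nurminen, Newcombe | 69.4% | 1.9% |

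Exact unconditional gives 67.8% to 69.4%, depending on the range of OR rates over which it is maximised. Wald and Farrington-Manning (FM) reach opposite conclusions with probability 21.7% at a 1% rate and 16.3% at 2%.

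**5. The other stated figures.** The 190 and 150 patients are read as totals (95 and 75 per arm), which fits the table.

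| Scenario | Wald power | Wald error | FM power | Ceiling, single point | Ceiling, OR 0–10% |
|---|---|---|---|---|---|
| 150/arm, 2%, margin 5% (stated 87%) | 87.7% | 4.5% | 72.4% | 84.3% | 76.9% |
| 95/arm, 1%, margin 5% | 93.3% | 7.8% | 62.5% | 77.2% | 70.5% |
| 75/arm, 1%, margin 6% | 89.8% | 6.6% | 66.5% | 77.2% | 71.7% |

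**The case against.** The 91% is not a miscalculation. It is right for a Wald 95% interval, and the protocol defines its test as a 95% interval compared with the margin. That is fair: the defect is that this interval misses its nominal level when events are sparse, and that the deciding interval is unnamed.

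The doubling of the error belongs to OR rates near 1% and below. At 5% the error is 2.9%, and the protocol cites literature rates up to 5% in one place and 10% in others. This also stands, but 1% is the rate the trial is planned on.

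The single-point ceiling comes from a test that ignores the OR arm, so it is a limit and not an attainable interval. On that basis the 87% claim falls short by only about 3 points (84.3%); the gap of about 10 points appears only when error is held over OR 0–10%.

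Finally, FM is conservative here. Adding one outcome to its acceptance region (1 OR, 2 ED infections) gives 77.8% power with error at most 2.43% over OR 0–10%. So 69% is not the only honest figure; about 68–78% is the range by method. None of this brings 91% within reach at 2.5%.

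**Conclusion.** The concern holds. At 150 per arm, with both rates 1% and a 4% margin, the stated level and the stated power are incompatible for every method. Wald delivers 91% with 5.2% error; a test held to 2.5% at the plan's boundary cannot exceed 83.3%, or 78.5% over OR rates of 0–10%. Methods that keep the level across that range give about 68–78%, a loss of roughly 13 to 23 points. The 87% claim and both fallback sizes have the same fault, to differing degrees. The result assumes equal true rates for power, 1:1 allocation and no dropout. That Wald was used is inferred from the table; the ceilings do not depend on that inference.

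**What to change.** Name one deciding interval in both Sample size assumptions and estimates and Data Analysis. For example: *Non-inferiority will be concluded if the upper limit of the two-sided 95% Farrington-Manning score interval for P_T − P_C is below 4%; Wald and other intervals are descriptive only.* Another method that keeps the level would also do, provided it is fixed in advance.

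Rerun the power table with that method and replace the text figures. With FM they become about 69% (1% rate, margin 4%), 54% (2%, margin 4%) and 72% (2%, margin 5%). Delete the 190- and 150-patient figures, or restate them as about 62% and 66% power.

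This costs only wording and a rerun. The sponsor must then choose. Staying at 300 patients means stating about 69% power. The projected 360 gives about 83% with FM, falling to 78% at 178 per arm because power moves in steps with whole-number counts. FM needs about 217–221 per arm (about 440 in total) for 90%. Even the best conceivable rule holding 2.5% over OR 0–10% needs about 200 per arm. Either figure exceeds the projected recruitment.
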